4.2. Inclusion Criteria

A subject will be eligible for inclusion in this study only if all the following criteria are met:

1. Subjects, ≥ 18 years old, must have a histologically confirmed diagnosis of sarcomas of the extremities (which may include gluteal muscle involvement) for which neoadjuvant radiation therapy followed by surgical resection is a planned intervention.
 - a. Subjects whose bowel cannot be completely protected from radiation exposure due to primary tumor location (e.g., proximal lower extremity) will be excluded.
2. Subjects must have one or more measurable target lesions by RECIST v1.1, assessed via CT scan or MRI.
3. At the time of study enrollment, subjects must have a tumor burden that is judged to be surgically resectable.
4. Subjects must have adequate organ function and blood chemistry and blood count parameters:
 - a. Absolute neutrophil count (ANC) $\geq 1500/\text{mm}^3$ ($\geq 1.5 \text{ GI/L}$) without granulocyte colony-stimulating factor support in the last 28 days.
 - b. White blood cell count $\geq 2500/\text{mm}^3$ ($\geq 2.5 \text{ GI/L}$).
 - c. Platelets $\geq 100,000/\text{mm}^3$ ($\geq 100 \text{ GI/L}$) without transfusion in the last 28 days.
 - d. Hemoglobin $\geq 9 \text{ g/dL}$ ($\geq 90 \text{ g/L}$) without transfusion in the last 28 days.
 - e. Alanine aminotransferase (ALT), aspartate aminotransferase (AST), and alkaline phosphatase (ALP) $\leq 3 \times$ upper limit of normal (ULN).
 - i. ALP $\leq 5 \times$ ULN is permitted in subjects with documented bone metastases (Phase 1 only).
 - f. Total bilirubin $\leq 1.5 \times$ ULN (for subjects with Gilbert's disease $\leq 3 \times$ ULN).
 - g. Serum albumin $\geq 2.8 \text{ g/dL}$.
 - h. Serum creatinine $\leq 2.0 \times$ ULN or calculated creatinine clearance $\geq 30 \text{ mL/min}$ ($\geq 0.5 \text{ mL/sec}$) using the Cockcroft-Gault equation:

Males: $(140 - \text{age}) \times \text{weight (kg)} / (\text{serum creatinine [mg/dL]} \times 72)$

Females: $[(140 - \text{age}) \times \text{weight (kg)} / (\text{serum creatinine [mg/dL]} \times 72)] \times 0.85$

- i. Urine protein/creatinine ratio (UPCR) $\leq 1 \text{ mg/mg} (\leq 113.2 \text{ mg/mmol})$.
5. Eastern Cooperative Oncology Group (ECOG) performance status 0 or 1.
6. Male or non-pregnant and non-breast feeding female:

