5. TABLE OF EVENTS

The schedule of assessments in Table 2 outlines the specific time points for study assessments.

Table 2. Schedule of Assessments

Assessments ^a	Baseline Screening ^b	Treatment Phase Cycle 1-3			Treatment Phase Cycle 4+	End of Treatment (EOT) Visit ^d	30 Day Safety Follow-Up ^p	Survival Follow-up
		D1	D8 ^c	D15 ^c	D1		(+/- 7 d)	
Informed Consent	X							
Medical History	X							
Hepatitis and HIV Screen ^e	X							
Urinalysis w/micro	X	X	X	X	X	X		
Urine Protein / Creatinine Ratio ^q	X							
TSH, Free T4	X	X			X	X		
Pregnancy Test ^f	X	X			X	X		
LVEF (echo or MUGA)	X							
12-lead ECG	X	X			X	X	X	
Physical Exam/ECOG	X	X	X	X	X	X	X	
Vital Signs, height, and weight ^g	X	X	X	X	X	X	X	
CBC/Diff/Blood Chem ^e	X	X	X	X	X	X	X	
Lipid Panel ^m	X	X			X	X		
Tissue Sample ⁿ	X ⁿ					X ⁿ		
Imaging ^h	X	Every 12 weeks (\pm 2 week).						
Cabozantinib ⁱ		Daily						
Radiation Therapy ^r		Administered per SOC. Radiation therapy to initiate within +7 days of C1D8.						
AE/Con Med Assessment ^j	X	Continuous from C1D1 through 30-day follow-up.						
Long Term Follow-up ^k								X

^a All treatment visits are allowed to occur in a window of ± 3 days unless otherwise specified.

^b Baseline screening visit will be done within 28 days prior to enrollment.

^c Day 8 and Day 15 visit is only in Cycle 1-3. Cycle 4+ will have visits on Day 1 only.

^d End of Treatment (EOT) Visit should be within 7 days of last study treatment (± 3 days).

^e Baseline HIV and Hepatitis screening to include HIV, HBV sAg, HBV cAb, and HCV Ab. See Table 3 for full Analyte Listing for CBC and chemistry panels.

^f For all female subjects of childbearing potential (see Inclusion 6), a serum pregnancy test will be done at all indicated timepoints. Pregnancy tests conducted after screening will be recorded in the source documentation only.

^g Height is measured only at screening. Vitals signs to include respiration rate, temperature, systolic/diastolic blood pressure, and pulse.

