- Local Laboratory Assessments: blood chemistry, complete blood count (CBC) + differential, complete urinalysis with microscopic evaluation, urine protein/creatinine ratio (UPCR), pregnancy test (women of child-bearing potential), HIV, hepatitis B surface antigen, hepatitis C antibody, fasting lipids, thyroid function

- CT or MRI must be done within the 28-day screening period, but preferably should be done as close to enrollment as possible
- Archival tissue collection (optional)

A subject is considered enrolled when the investigator decides that the subject has met all eligibility criteria. The investigator is to document this decision and date, in the subject's medical record and/or in/on the electronic case report form (eCRF). Subjects should initiate treatment within 14 days of being enrolled to the study (28-day screening window from date of consent to enrollment date, plus up to an additional 14 days from enrollment date to C1D1 [total elapsed time from initiating screening to initiating therapy may not exceed 42 days]).

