10.2.2. Adverse Event Management Algorithms

Table 8 - Management Guidelines for Adverse Events Possibly Related to Cabozantinib

System/Organ	Adverse Event	CTCAE Grade v5.0	Dose modification Algorithm
Skin/Mucosa	Palmar-plantar Erythrodysesthesia Syndrome	Grade 1	If PPES is clinically insignificant and tolerable, cabozantinib may be continued at current dose, otherwise reduce by one dose level. Urea 20% cream twice daily and Clobetasol 0.05% cream once daily to be reassessed at least weekly. If PPES does not improve, or worsens after 2 weeks, follow intervention guidelines for grade 2.
		Grade 2	Cabozantinib treatment may be continued if PPES is tolerated. Cabozantinib should be dose reduced or interrupted if PPES is intolerable. Continue urea 20% cream twice daily AND high potency steroid cream (e.g., clobetasol 0.05%) once daily and add analgesics (e.g., NSAIDs/gamma-aminobutyric acid agonists) for pain control if needed. Reassess at least weekly; if PPES worsens or affects self-care, proceed to the intervention guidelines for Grade 3.
		Grade 3+	Interrupt cabozantinib treatment until severity decreases to Grade 1 or 0. Continue treatment of skin reaction with high potency steroid cream (e.g., clobetasol 0.05%) twice daily AND analgesics. Resume study drug at a reduced dose if PPES recovers to Grade ≤ 1. Discontinue subject from study treatment if PPES does not improve within 6 weeks.

	Stomatitis and/or Mucositis	Any Grade	
No change in cabozantinib treatment. Preventive measures may include a comprehensive oral examination to identify and treat any potential risk for complications before study treatment is initiated. Appropriate correction of local factors should be instituted as indicated, such as modification of ill-fitting dentures and appropriate care of gingivitis. During treatment with cabozantinib, good oral hygiene and standard local treatments such as non-traumatic and non-irritating cleansing, and oral rinses (e.g., with a weak solution of salt and baking soda) should be maintained. Lips should be kept moisturized with lip balm. The use of lipstick, lip-gloss, and Vaseline should be avoided.
 
Local treatment should be instituted at the earliest onset of symptoms. Obtain bacterial/viral culture if oral infection is suspected and treat infection as clinically indicated.

Lab Abnormalities	Proteinuria	UPC Ratio \leq 1 mg/mg (\leq 113.1 mg/mmol)	
No change in cabozantinib treatment or monitoring

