		For UPC Ratio >1 and <3.5 mg/mg (>113.1 and <395.9 mg/mmol)	
Consider confirming with a 24-h protein assessment within 7 days
 
No change in cabozantinib treatment required if UPCR \leq 2 mg/mg or urine protein \leq 2 g/24 h on 24-h urine collection.
 
Dose reduce or interrupt cabozantinib treatment if UPCR $>$ 2 mg/mg on repeat UPCR testing or urine protein $>$ 2 g/24 h on 24-h urine collection.
 
Continue cabozantinib on a reduced dose if UPCR decreases to $<$ 2 mg/mg.

		
Consider interrupting cabozantinib treatment if UPCR remains $> 2 \text{ mg/mg}$ despite a dose reduction until UPCR decreases to $< 2 \text{ mg/mg}$. Restart cabozantinib treatment at a reduced dose after a dose interruption.
 
Repeat UPCR within 7 days and once per week. If UPCR $< 1 \text{ mg/mg}$ on 2 consecutive readings, UPCR monitoring can revert to protocol-specific times. (Second reading is confirmatory and can be done within 1 week of first reading.)
 
If UPCR remains $> 1 \text{ mg/mg}$ and $< 2 \text{ mg/mg}$ for 1 month or is determined to be stable (< 20% change) for 1 month, check urine protein/creatinine per protocol or as clinically indicated.

	UPC Ratio $\geq 3.5 \text{ mg/mg}$ ($\geq 395.9 \text{ mg/mmol}$)	
Interrupt cabozantinib treatment pending repeat UPCR within 7 days and/or 24 h urine protein.
 
If $\geq 3.5 \text{ mg/mg}$ on repeat UPCR, continue to interrupt cabozantinib treatment and check UPCR every 7 days. If UPCR decreases to $< 2 \text{ mg/mg}$, restart cabozantinib treatment at a reduced dose and monitoring of urine protein/creatinine should continue weekly until the UPCR decreases to $< 1 \text{ mg/mg}$.
 
If UPCR remains $> 1 \text{ mg/mg}$ and $< 2 \text{ mg/mg}$ for 1 month or is determined to be stable (< 20% change) for 1 month, check urine protein/creatinine per protocol or as clinically indicated.

	Nephrotic Syndrome	Discontinue cabozantinib.

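### UPCR, which mainly drives the proteinuria dose steps, is scheduled only at screening with no urinalysis result to prompt it; separately, the chemistry panel omits magnesium and phosphate

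*Combined protocol and SAP*

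**What the plan says.** **Schedule.** In Table 2 (Section 5) the row "Urine Protein / Creatinine Ratio" is marked in the screening column and nowhere else. Section 6.1 also lists the test at screening. The Day 1, Day 8, Day 15 and EOT lists (Sections 6.2.2 to 6.2.4 and 6.3) ask for urinalysis with microscopy and not UPCR. The 30-day visit (Section 6.4.1) has no urine test. Footnote c adds that "Cycle 4+ will have visits on Day 1 only".

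**Dose rules.** Inclusion criterion 4i requires a UPCR of at most 1 mg/mg, so every subject begins in the Table 8 row that reads "No change in cabozantinib treatment or monitoring". Above 1 mg/mg the instruction is "Repeat UPCR within 7 days and once per week". A repeat UPCR above 2 mg/mg, or more than 2 g in a 24-hour collection, leads to reduction or interruption; 3.5 mg/mg or more leads to interruption. There are two ways out of weekly testing. After two consecutive values below 1 mg/mg, "UPCR monitoring can revert to protocol-specific times". After a month between 1 and 2 mg/mg, or a stable month, "check urine protein/creatinine per protocol or as clinically indicated".

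**Electrolytes.** Footnote e of Table 2 names Table 3 as the full listing for the chemistry panel. It contains neither magnesium nor phosphate. Section 10.2.1 includes low magnesium and low phosphate among laboratory adverse events affecting at least 5% of cabozantinib-treated subjects. The electrolyte row of Table 8 names both and asks for frequent monitoring.

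**The concern.** The dose rule is written in one measurement and the visit schedule supplies another. A site that follows Table 2 exactly would see urine protein on urinalysis but would never obtain the ratio that Table 8 compares with its cut-offs. The step from a positive urinalysis to a quantitative test is not written anywhere, so two subjects with the same proteinuria could reach a dose reduction at different times because their clinicians ordered the test at different times.

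Section 10.2.1 calls proteinuria medically important, though less frequent, and makes nephrotic syndrome a reason to stop the drug. The lower UPCR steps allow action before that point.

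For magnesium and phosphate, Section 9.2.1 records every Grade 2 or higher laboratory abnormality as an adverse event, but only a measured abnormality can be recorded. Section 12.1 reports laboratory abnormalities and dose modifications, and safety and tolerability is a secondary endpoint, so uneven measurement carries through to reported results.

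**Working it through.** The plan gives no figure to reproduce. The check is a cross-reading of Tables 2, 3 and 8 with the visit lists, followed by a count.

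**Could the single UPCR mark be a broken table?** Unlikely. The separate lists in Section 6 agree with it.

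**Does other text fill the gap?**
- Footnote q of Table 2 starts from a UPCR that is already abnormal and leads to a 24-hour collection. It does not start from a urinalysis result.
- Section 9.2.1 asks for laboratory review by standard clinical practice, with no trigger.
- The QTc row of Table 8 is a useful contrast. It also returns subjects to the usual timepoints, and Table 2 does schedule ECGs on Day 1 of each cycle and at EOT. The UPCR reference has no such target.

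**Count over six 21-day cycles in total (6 × 21 = 126 days):**
- Urinalyses after screening: 3 cycles × 3 visits + 3 cycles × 1 visit + EOT = 9 + 3 + 1 = 13.
- Chemistry panels after screening: 13 + the 30-day visit = 14.
- UPCRs after screening: 0.
- Panels naming magnesium or phosphate: 0, baseline included. Table 3 has 18 chemistry analytes and neither is among them.

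**Count on the typical surgical timeline (Section 6.2.1: radiotherapy 5-6 weeks, surgery 4-6 weeks later, drug stopped at least 28 days before surgery):**
- Shortest: radiotherapy on days 8-42, surgery on day 42 + 28 = 70, last dose on day 70 − 28 = 42, the end of Cycle 2. Urinalyses 6 + 1 = 7; chemistry panels 8.
- Longest: radiotherapy on days 15-56, surgery on day 56 + 42 = 98, last dose on day 98 − 28 = 70, which is Cycle 4 Day 7. Urinalyses 9 + 1 + 1 = 11; chemistry panels 12.

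Subtract one of each wherever Cycle 1 Day 1 tests are waived because screening fell within 72 hours (Section 6.2.2).

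**Tests under a Day 1 plus EOT schedule:** six cycles, 6 + 1 = 7; shortest typical course, 2 + 1 = 3; longest, 4 + 1 = 5.

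**Weekly repeats falling between visits.** In Cycles 1-3 weekly tests coincide with Days 1, 8 and 15. From Cycle 4 the visits are on days 64, 85 and 106, so weekly tests started on day 64 fall between visits on days 71, 78, 92, 99, 113 and 120: six in all. If the one-month exit is met, only days 71, 78 and 92 remain: three.

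**The case against.** The strongest reply is that proteinuria is watched closely. Urine protein is part of the urinalysis in Table 3 and, on the typical timeline, is checked about weekly for almost all of the dosing period. A competent investigator who sees protein will quantify it. Table 8 is management guidance for a suspected toxicity and not a visit calendar, and it sets its own weekly timing once UPCR exceeds 1 mg/mg.

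Much of this stands, and it rules out three stronger readings that a reader might infer:

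- *That proteinuria goes unmonitored on treatment.* It does not; urinalysis is a scheduled route to detection. Only the link to the quantitative test is missing.
- *That the dose rules cannot operate.* They can. A UPCR may be ordered at discretion, 24-hour protein is accepted for some actions, nephrotic syndrome has its own row, and Section 7.1.2 allows grade-based or discretionary dose changes. However, the note to Table 6 refers condition-specific criteria to Section 10.2.2, where the proteinuria thresholds are mainly UPCR values.
- *That both exits from weekly testing lead nowhere.* The one-month exit also allows testing on clinical indication. Only the exit after two values below 1 mg/mg lacks any target.

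On electrolytes, the reply is that sodium, potassium, chloride, bicarbonate and calcium are all scheduled, that magnesium is checked after Grade 3 QTc prolongation, and that neither missing analyte has a specific dose threshold. That is correct, and it limits this part to monitoring and ascertainment. It does not reconcile a request for frequent monitoring that names both disorders with a panel that measures neither.

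**Conclusion.** The point holds as a cheap improvement to safety monitoring. Detection of urine protein is scheduled; its quantification against the dose steps is not. After screening there are no scheduled UPCRs, against 13 urinalyses over six cycles or 7-11 on the typical surgical timeline. Magnesium and phosphate have no named visit, against 14 chemistry panels over six cycles or 8-12 on the typical timeline.

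The counts read the six-cycle maximum in Section 6.2.1 as a total. At 126 days, about four months, this fits the five months of treatment estimated in Section 3.3.

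Two further inferences are not supported. A reader might expect the recommended Phase 2 dose to be affected, but Section 10.2.1 limits DLTs to toxicity in the irradiated region, so DLTs are unaffected, as are alpha, power and sample size. A reader might also want a number of missed adverse events. None can be derived, because the 5% threshold in Section 10.2.1 is not grade-specific and does not come from this regimen.

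**What to change.** 1. In Table 2, either schedule UPCR on Day 1 of each cycle and at EOT, or require a reflex UPCR at a urinalysis protein level that the sponsor names. Either gives Table 8's return to scheduled monitoring a meaning. The Table 8 thresholds need not change.
2. Reconcile footnote q with Table 8. The footnote says an abnormal UPCR should lead to a 24-hour collection, while Table 8 only asks for confirmation to be considered above 1 mg/mg. Without a change, on-treatment UPCRs would extend the stricter instruction to every cycle. Limit the footnote to screening, or align it with Table 8.
3. Add magnesium and phosphate to the Table 3 chemistry panel, baseline included.

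**Cost.** The routine or reflex tests use urine and blood already collected. The fixed schedule adds 7 UPCRs over six cycles, or 3-5 on the typical surgical timeline. The reflex option adds up to 13 over six cycles if protein is persistently positive. Magnesium and phosphate are added to up to 14 on-study panels plus baseline. The downsides are small laboratory charges, some extra recording of low-grade adverse events and, for subjects found above 1 mg/mg, the weekly repeats that Table 8 already requires. If these begin at Cycle 4 Day 1, up to six fall between visits through Cycle 6, or three if the one-month exit is met.

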10.2.3. Cabozantinib Dose Reinstitution and Reescalation

If the subject recovers from his or her toxicities to CTCAE v.5.0 Grade \leq 1 or to the baseline value (or lower) and the toxicity was unrelated to study treatment, then study treatment may be restarted with no change in dose.

If the subject recovers from his or her toxicities to Grade \leq 1 or to the baseline value (or lower) the toxicity was deemed possibly related to study treatment, then study treatment may be restarted as outlined in Table 5 and 6.

Subjects receiving a dose of 20 mg daily may be restarted at the same dose if deemed safe at the discretion of the Sponsor-Investigator or treating Sub-Investigator. Subjects unable to tolerate a dose of 20 mg daily should discontinue study treatment.

10.2.4. Dose re-escalation is not permitted. Overdose

Any overdose, or study drug administration error that results in an AE, even if it does not meet the definition of serious, requires reporting within one (1) business day to Exelixis.

10.3. Radiation Therapy Related Toxicity

The expected toxicities related to radiation therapy may vary in relation to the site of irradiation. The most commonly observed toxicities include fatigue (Grade 3), and skin toxicities (Grade 3) such as rash, color changes, burning, blistering, or desquamation. Skin toxicities should be managed by radiation-oncology staff utilizing standard of care protocols.

The radiation oncologist may list expected toxicities for a given radiation treatment prior to administration of radiation treatment in the subject's medical record. Strict prospective quality assurance of all radiation plans will be performed prior to initiation of radiotherapy, per institutional standards, to minimize risk of serious toxicity.

Toxicities of radiation should be treated according to standard institutional practices, including the prescription of steroids, if appropriate. Subjects will continue study treatment if steroids are used to treat radiation-associated toxicity.

11. CONCOMITANT MEDICATIONS AND PROCEDURES

All concomitant treatments, including blood and blood products, must be reported on the eCRF. Throughout the study, investigators may prescribe any concomitant medications or treatments deemed necessary to provide adequate supportive care except for those listed in Section 11.2.

Concomitant therapies are to be collected from enrollment/randomization through the EOT Visit. Therapy name including indication, dose, frequency, route, start date and stop date will be recorded on each subject's CRF(s).

11.1. Permitted Medications and Procedures

The investigator must be informed as soon as possible about any medication taken from the time of screening until the 30 Day Follow-Up visit. Any concomitant medication(s), including herbal preparations, taken during the study will be recorded in the CRF. The minimum requirement is that drug name, dose, and the dates of administration are to be recorded. Additionally, a complete list of all prior cancer therapies will be recorded in the CRF.

Subjects should receive full supportive care during the study, including transfusions of blood and blood products, and treatment with antibiotics, anti-emetics, anti-diarrheas, and analgesics, and other care as deemed appropriate, and in accordance with their institutional guidelines. WBC growth factors may be administered at the discretion of the investigator, consistent with institutional guidelines.

Extreme precaution must be taken with contraceptives (either combined or progesterone only), as it is not known if there is the potential of inhibition/induction of enzymes that affect the metabolism of estrogens and/or progestins.

- Antiemetics and antidiarrheal medications are allowed prophylactically according to standard clinical practice if clinically indicated.
- Granulocyte colony-stimulating factors (G-CSF or GM-CSF) are allowed if used per clinical guidelines (e.g., ASCO or ESMO guidelines).
- Bisphosphonates can be used to control bone loss or hypocalcemia if the benefit outweighs the risk per the investigator's discretion.
- Transfusions and hormone replacement should be utilized as indicated by standard clinical practice.
- Individualized anticoagulation therapy with heparin is allowed if it can be provided safely and effectively under the following circumstances:
 - *Low dose heparins for prophylactic use* are allowed if clinically indicated and the benefit outweighs the risk per the investigator's discretion.
 - *Therapeutic doses of LMWH at the time of the first dose of study treatment* are allowed if the subject has no evidence of brain metastasis, has been on a stable dose of LMWH for at least 6 weeks, and has had no complications from a thromboembolic event or the anticoagulation regimen.

- *Therapeutic doses of LMWH after first dose of study treatment* are allowed if clinically indicated (e.g., for the treatment of deep venous thrombosis), and the benefit outweighs the risk per the investigator's discretion. For management of thromboembolic complications while on study, refer to Section 10.2.2.
- Accepted clinical guidelines regarding appropriate management while receiving anticoagulation therapy with heparins must be followed. This includes, but is not limited to, subject education regarding potential adverse drug reactions, monitoring laboratory parameters, dose adjustments (e.g., due to kidney dysfunction).
- For restrictions on oral anticoagulants see Section 11.2.

Potential drug interactions with cabozantinib are summarized in Section 11.3.

